### Acetylcholinesterase Inhibition AESIs

AEs will be regarded as Acetylcholinesterase Inhibition AESIs if the preferred terms are any one of the following PTs below.

Term	Code	Term	Code
Atrioventricular block first degree	10003674	Convulsions local	10010920
Atonic seizures	10003628	Diarrhoea	10012735
Bradycardia foetal	10006094	Status epilepticus	10041962
Diarrhoea haemorrhagic	10012741	Laryngeal dyspnoea	10052390
Dysarthria	10013887	Prophylaxis against bronchospasm	10054927

Term	Code	Term	Code
Dyspnoea paroxysmal nocturnal	10013974	Post procedural diarrhoea	10057585
Retching	10038776	Procedural vomiting	10066963
Simple partial seizures	10040703	Idiopathic generalised epilepsy	10071081
Sinus bradycardia	10040741	Bradycardia	10006093
Vomiting projectile	10047708	Convulsive threshold lowered	10010927
Self-induced vomiting	10048636	Diarrhoea infectious neonatal	10012744
Hypoglycaemic seizure	10048803	Dyspnoea at rest	10013969
Lennox-Gastaut syndrome	10048816	Frequent bowel movements	10017367
Nocturnal dyspnoea	10049235	Haematemesis	10018830
Atypical benign partial epilepsy	10056699	Nausea	10028813
Hyponatraemic seizure	10073183	Tonic convulsion	10043994
Infantile vomiting	10075315	Frontal lobe epilepsy	10049424
Neonatal sinus bradycardia	10082188	Tonic clonic movements	10051171
Abdominal discomfort	10000059	Clonic convulsion	10053398
Defaecation urgency	10012110	Lafora's myoclonic epilepsy	10054030
Drooling	10013642	Psychogenic seizure	10058895
Epilepsy	10015037	Partial seizures	10061334
Flatulence	10016766	Seizure like phenomena	10071048
Heart rate decreased	10019301	Change in seizure presentation	10075606
Hyperkinesia	10020651	Idiopathic partial epilepsy	10076552
Petit mal epilepsy	10034759	Post stroke seizure	10076981
Psychomotor hyperactivity	10037211	Abdominal pain lower	10000084
Vomiting	10047700	Cold sweat	10009866
Myoclonic epilepsy	10054859	Diarrhoea infectious	10012742
Partial seizures with secondary generalisation	10056209	Dyspnoea exertional	10013971
Alcoholic seizure	10056347	Febrile convulsion	10016284
Therapeutic emesis	10058324	Generalised tonic-clonic seizure	10018100
Faecal vomiting	10064670	Night sweats	10029410
Psychogenic pseudosyncope	10075190	Presyncope	10036653
Central bradycardia	10078310	Sweat gland disorder	10042653
Gastrointestinal disorder	10017944	Bradyarrhythmia	10049765
Hyperemesis gravidarum	10020614	Convulsion in childhood	10052391
Lacrimation decreased	10023642	Prophylaxis of nausea and vomiting	10054133
Vomiting psychogenic	10047709	Increased bronchial secretion	10062530
Wheezing	10047924	Transfusion-associated dyspnoea	10072266
Viral diarrhoea	10051511	Hypocalcaemic seizure	10072456
Epigastric discomfort	10053155	Abdominal pain	10000081
Antidiarrhoeal supportive care	10055660	Abdominal pain upper	10000087
Bronchial hyperreactivity	10066091	Bronchospasm	10006482
Gastrointestinal tract irritation	10070840	Gastrointestinal pain	10017999

Term	Code	Term	Code
Focal dyscognitive seizures	10079424	Hyperhidrosis	10020642
Febrile infection-related epilepsy syndrome	10079438	Salivary hypersecretion	10039424
Neonatal epileptic seizure	10082068	Seizure	10039906
Gelastic seizure	10082918	Sweating fever	10042666
Abdominal tenderness	10000097	Syncope	10042772
Drug withdrawal convulsions	10013752	Bradycardia neonatal	10056471
Dyspnoea	10013968	Acetonaemic vomiting	10058938
Lacrimation increased	10023644	Abdominal symptom	10060926
Seizure anoxic	10039907	Cyclic vomiting syndrome	10062937
Autonomic seizure	10049612	Prophylaxis against diarrhoea	10064065
Benign familial neonatal convulsions	10067866	Post-tussive vomiting	10066220
Hyperglycaemic seizure	10071394	Procedural nausea	10066962
Unilateral bronchospasm	10072338	Seizure cluster	10071350
Faeces soft	10074859	Migraine-triggered seizure	10076676
Irregular breathing	10076213	Acute encephalitis with refractory, repetitive partial seizures	10076948
Asthma	10003553	Discoloured vomit	10079120
Bacterial diarrhoea	10004016	Epilepsy with myoclonic-ataxic seizures	10081179
Bronchospasm paradoxical	10006486	Seizure prophylaxis	10081601
-	-	Neonatal seizure	10082067

### 6.2.2.2. Renal impairment

The severity of renal impairment will be evaluated using estimated by creatinine clearance (Ccr).

Severity of renal impairment will be categorized based on creatinine clearance as below (rounded to the nearest integer):

- Normal ( $\geq 90 \text{ mL/min}$ )
- Mild ( $\geq 60 \text{ to } 89 \text{ mL/min}$ )
- Moderate ( $\geq 30 \text{ to } 59 \text{ mL/min}$ )
- Severe ( $< 30 \text{ mL/min}$ )

### 6.2.3. Criteria for Potential Clinical Importance

#### 6.2.3.1. ECG

ECG Parameter	Units	Potential Clinically Important Range	
		Lower	Upper
Absolute			
Absolute QTc Interval	msec	N/A	>450
Absolute PR Interval	msec	< 110	> 220
Absolute QRS Interval	msec	< 75	> 110

#### 6.2.3.2. Vital Signs

Vital Sign Parameter (Absolute)	Units	Potentially Clinically Important Range	
		Lower	Upper
Systolic Blood Pressure	mmHg	< 85	> 160
Diastolic Blood Pressure	mmHg	< 45	> 100
Pulse Rate	bpm	< 40	> 110

## 6.2.4. Division of Microbiology and Infectious Diseases Adult Toxicity Tables for Adverse Event Assessment

### 6.2.4.1. Laboratory Values

For grading, only numerical criteria will be used in the derivation rules as follows.

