SERIOUS OR LIFE-THREATENING AEs: ANY clinical event deemed by the investigator to be serious or life-threatening should be considered a Grade 4 event. Clinical events considered to be serious or life-threatening include, but are not limited to: seizures, coma, tetany, diabetic ketoacidosis, disseminated intravascular coagulation, diffuse petechiae, paralysis, acute psychosis, and severe depression.

COMMENTS REGARDING THE USE OF THESE TABLES

- Standardized and commonly used toxicity tables (Division of AIDS, National Cancer Institute's Common Toxicity Criteria, and World Health Organization) have been adapted for use by the Division of Microbiology and Infectious Diseases (DMID) and modified to better meet the needs of participants in Division of Microbiology and Infectious Diseases (DMID) trials.
- For parameters not included in the following Toxicity Tables, study sites should refer to the "Guide for Estimating Severity Grade" located above.
- Criteria are generally grouped by body system.

Note: Adult DMID toxicity criteria will be applied for all laboratory parameters, with the exception of serum creatinine adolescent laboratory data, which will be assessed using paediatric DMID toxicity criteria.

HEMATOLOGY				
	Grade 1	Grade 2	Grade 3	Grade 4
Hemoglobin	9.5 to 10.5 g/dL	8.0 to 9.4 g/dL	6.5 to 7.9 g/dL	<6.5 g/dL
Absolute Neutrophil Count	1000 to 1500 /mm ³	750 to 999 /mm ³	500 to 749 /mm ³	<500 /mm ³
Platelets	75,000 to 99,999 /mm ³	50,000 to 74,999 /mm ³	20,000 to 49,999 /mm ³	<20,000 /mm ³
White Blood Cells	11,000 to 13,000 /mm ³	13,000 to 15,000 /mm ³	15,000 to 30,000 /mm ³	>30,000 or <1000 /mm ³
% Polymorphonuclear Leukocytes + Band Cells	>80%	90 to 95%	>95%	N/A
Abnormal Fibrinogen	Low: 100 to 200 mg/dL High: 400 to 600 mg/dL	Low: <100 mg/dL High: >600 mg/dL	Low: <50 mg/dL High: N/A	Fibrinogen associated with gross bleeding or with disseminated coagulation
Fibrin Split Product	20 to 40 µg/mL	41 to 50 µg/mL	51 to 60 µg/dL	>60 µg/dL
Prothrombin Time (PT)	1.01 to 1.25 x ULN	1.26 to 1.5 x ULN	1.51 to 3.0 x ULN	>3 x ULN
Activated Partial Thromboplastin (APTT)	1.01 to 1.66 x ULN	1.67 to 2.33 x ULN	2.34 to 3 x ULN	>3 x ULN
Methemoglobin	5.0 to 9.9%	10.0 to 14.9%	15.0 to 19.9%	>20%

N/A = not applicable; ULN = upper limit of normal.

CHEMISTRIES				
	Grade 1	Grade 2	Grade 3	Grade 4
Hyponatremia	130 to 135 mEq/L	123 to 129 mEq/L	116 to 122 mEq/L	<116 mEq/L or abnormal sodium with mental status changes or seizures

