### **4.6.3. Additional Safety Assessments**

#### **4.6.3.1. Laboratory Data**

Summaries of worst-case grade increase from baseline grade will be provided for all the lab tests that are gradable by DMID criteria (Section 6.2.4). These summaries will display the number and percentage of subjects with a maximum post-baseline grade increasing from their baseline grade. Any increase in grade from baseline will be summarized along with any increase to a maximum grade of 3 and any increase to a maximum grade of 4. Missing baseline grade will be assumed as grade 0. For laboratory tests that are graded for both low and high values, summaries will be done separately and labelled by direction, e.g., sodium will be summarized as hyponatremia and hypernatremia separately. The determination of worst case post-baseline takes into account both planned and unscheduled assessments.

For lab tests that are not gradable by DMID criteria (Section 6.2.4), summaries of worst-case changes from baseline with respect to normal range will be generated. Decreases to low, changes to normal or no changes from baseline, and increases to high will be summarized for the worst-case post-baseline. If a subject has a decrease to low and an increase to high during the same time interval, then the subject is counted in both the “Decrease to Low” categories and the “Increase to High” categories.

Separate summary tables for change from baseline in haematology, and chemistry laboratory tests will be produced. Liver function laboratory tests will be included with chemistry lab tests.

A summary of Liver Monitoring/Stopping Event Reporting will be summarized. For participants with more than one liver stopping or liver monitoring event, only data related to the earliest most severe criteria event is included in the summary.

Abnormal liver chemistry results will be summarized by increasing folds above the upper limit of normal (ULN) including tests of interest and thresholds as follows (including data at all the visit including unscheduled visits):

- ALT or AST > 3xULN and Total Bilirubin > 2xULN\*
- ALT or AST > 3xULN and ALP < 2xULN and Total Bilirubin  $\geq$  2xULN
- ALT or AST > 3xULN and Total Bilirubin > 1.5xULN
- Hepatocellular injury:  $(ALT/ALT\ ULN)/(ALP/ALP\ ULN) \geq 5$  and ALT  $\geq$  3xULN \*\*
- ALT or AST  $\geq$  20xULN
- ALT or AST  $\geq$  10xULN
- ALT or AST  $\geq$  8xULN
- ALT or AST  $\geq$  5xULN
- ALT or AST  $\geq$  3xULN
- ALT  $\geq$  20xULN
- ALT  $\geq$  10xULN

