#### Adults:

For adults, laboratory abnormalities will be graded according to the modified US National Institute of Allergy and Infectious Diseases Division of Microbiology and Infectious Diseases (DMID) criteria, which is aligned with the global studies (204989 and 212390). Laboratory results are converted to SI units.

HEMATOLOGY						
	Laboratory parameter	Display label	Grade 1	Grade 2	Grade 3	Grade 4
Hemoglobin	Hemoglobin	Hemoglobin (Low)	9.5 to 10.5 g/dL	8.0 to 9.4 g/dL	6.5 to 7.9 g/dL	<6.5 g/dL
Absolute Neutrophil Count	Neutrophils	Neutrophils (Low)	1000 to 1500 /mm 	750 to 999 /mm 	500 to 749 /mm 	<500 /mm 
Platelets	Platelets	Platelets (Low)	75,000 to 99,999 /mm 	50,000 to 74,999 /mm 	20,000 to 49,999 /mm 	<20,000 /mm 
White Blood Cells	Leukocytes	Leukocytes (High)	11,000 to 13,000 /mm 	13,001 to 15,000 /mm 	15,001 to 30,000 /mm 	>30,000 or <1000 /mm 
% Polymorphonuclear Leukocytes + Band Cells	NA	NA	>80%	90 to 95%	>95%	N/A
Abnormal Fibrinogen	NA	NA	Low: 100 to 200 mg/dL High: 400 to 600 mg/dL	Low: <100 mg/dL High: >600 mg/dL	Low: <50 mg/dL High: N/A	Fibrinogen associated with gross bleeding or with disseminated coagulation
Fibrin Split Product	NA	NA	20 to 40 mcg/mL	41 to 50 mcg/mL	51 to 60 mcg/dL	>60 mcg/dL
Prothrombin Time (PT)	NA	NA	1.01 to 1.25 × ULN	1.26 to 1.5 × ULN	1.51 to 3.0 × ULN	>3 × ULN
Activated Partial Thromboplastin (APTT)	NA	NA	1.01 to 1.66 × ULN	1.67 to 2.33 × ULN	2.34 to 3 × ULN	>3 × ULN
Methemoglobin	NA	NA	5.0 to 9.9%	10.0 to 14.9%	15.0 to 19.9%	>20%

N/A=not applicable; ULN=upper limit of normal.

CHEMISTRIES						
	Laboratory parameter	Display label	Grade 1	Grade 2	Grade 3	Grade 4
Hyponatremia	Sodium	Sodium (Low)	130 to 135 mEq/L	123 to 129 mEq/L	116 to 122 mEq/L	<116 mEq/L or abnormal sodium with mental status changes or seizures
Hypernatremia	Sodium	Sodium (High)	146 to 150 mEq/L	151 to 157 mEq/L	158 to 165 mEq/L	>165 mEq/L or abnormal sodium with mental status changes or seizures
Hypokalemia	Potassium	Potassium (Low)	3.0 to 3.4 mEq/L	2.5 to 2.9 mEq/L	2.0 to 2.4 mEq/L or intensive replacement therapy of hospitalization required	<2.0 mEq/L or abnormal potassium with paresis, ileus, or life-threatening arrhythmia

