Hyperkalemia	Potassium	Potassium (High)	5.6 to 6.0 mEq/L	6.1 to 6.5 mEq/L	6.6 to 7.0 mEq/L	>7.0 mEq/L or abnormal potassium with life-threatening arrhythmia
Hypoglycemia	Glucose	Glucose (Low)	55 to 64 mg/dL	40 to 54 mg/dL	30 to 39 mg/dL	<30 mg/dL or abnormal glucose with mental status changes or coma
Hyperglycemia (nonfasting and no prior diabetes)	Glucose	Glucose (High)	116 to 160 mg/dL	161 to 250 mg/dL	251 to 500 mg/dL	>500 mg/dL or abnormal glucose with ketoacidosis or seizures
Hypocalcemia (corrected for albumin)	Calcium	Calcium (Low)	8.4 to 7.8 mg/dL	7.7 to 7.0 mg/dL	6.9 to 6.1 mg/dL	<6.1 mg/dL or abnormal calcium with life-threatening arrhythmia or tetany
Hypercalcemia (corrected for albumin)	Calcium	Calcium (High)	10.6 to 11.5 mg/dL	11.6 to 12.5 mg/dL	12.6 to 13.5 mg/dL	>13.5 mg/dL or abnormal calcium with life-threatening arrhythmia
Hypomagnesemia	Magnesium	Magnesium (Low)	1.4 to 1.2 mEq/L	1.1 to 0.9 mEq/L	0.8 to 0.6 mEq/L	<0.6 mEq/L or abnormal magnesium with life-threatening arrhythmia
Hypophosphatemia	Phosphate	Phosphate (Low)	2.0 to 2.4 mg/dL	1.5 to 1.9 mg/dL or replacement Rx required	1.0 to 1.4 mg/dL intensive therapy or hospitalization required	<1.0 mg/dL or abnormal phosphate with life-threatening arrhythmia

CHEMISTRIES						
	Laboratory parameter	Display label	Grade 1	Grade 2	Grade 3	Grade 4
Hyperbilirubinemia (when accompanied by any increase in other liver function test)	Bilirubin (when any of AST, ALT and ALP is greater than the upper limit of normal range at the same analysis visit)	Bilirubin (High)	1.1 to <1.25 × ULN	1.25 to <1.5 × ULN	1.5 to 1.75 × ULN	>1.75 × ULN
Hyperbilirubinemia (when other liver function tests are in the normal range)	Bilirubin (when all of AST, ALT and ALP are within the normal range at the same analysis visit)	Bilirubin (High)	1.1 to <1.5 × ULN	1.5 to <2.0 × ULN	2.0 to 3.0 × ULN	>3.0 × ULN
Blood urea nitrogen	Urea	Urea Nitrogen (High)	1.25 to 2.5 × ULN	2.6 to 5 × ULN	5.1 to 10 × ULN	>10 × ULN
Hyperuricemia (uric acid)	NA	NA	7.5 to 10.0 mg/dL	10.1 to 12.0 mg/dL	12.1 to 15.0 mg/dL	>15.0 mg/dL
Creatinine	Creatinine	Creatinine (High)	1.1 to 1.5 × ULN	1.6 to 3.0 × ULN	3.1 to 6.0 × ULN	>6 × ULN or dialysis required

Rx=therapy; ULN=upper limit of normal

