**Adolescent Participants:**

For adolescent participants over 12 years of age and less than 18 years of age, the adult DMID will be applied for all parameters with the exception of serum creatinine which will be graded programmatically according to the modified DMID pediatric toxicity criteria , which is aligned with the global studies (204989 and 212390) . Laboratory results are converted to SI units.

CHEMISTRIES						
	Laboratory parameter	Display label	Grade 1	Grade 2	Grade 3	Grade 4
Creatinine	Creatinine	Creatinine (High)	1.0 to 1.7 x ULN	1.8 to 2.4 x ULN	2.5 to 3.5 x ULN	>3.5 x ULN

ULN=upper limit of normal.

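### Applied literally, the SAP's laboratory grade table labels a leukocyte count below 1000/mm³ as high and leaves narrow creatinine and urea intervals without a grade

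*SAP*

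**What the plan says.** SAP 6.2.4.1 turns the modified DMID toxicity table into programming rules: "For grading, only numerical criteria will be used in the derivation rules as follows". Each graded test has a laboratory parameter and a display label.

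- **Leukocytes.** There is one row, labelled *Leukocytes (High)*. Grades 1 to 3 are high counts only; the Grade 4 cell is ">30,000 or <1000" /mm³. Protocol 10.12 (Appendix 12) has the same Grade 4 cell, ">30,000 or <1000 /mm"³, but no direction label.
- **Direction rule.** SAP 4.6.3.1: "For laboratory tests that are graded for both low and high values, summaries will be done separately and labelled by direction". Sodium, potassium, glucose and calcium each have a Low and a High row; leukocytes do not.
- **Ratios to ULN.** Urea Grade 1 is "1.25 to 2.5 × ULN" and Grade 2 starts at 2.6. Adult creatinine goes 1.1–1.5, 1.6–3.0, 3.1–6.0, >6. Adolescent creatinine goes 1.0–1.7, then "1.8 to 2.4 x ULN", then 2.5–3.5, >3.5.
- **Age.** The adolescent paragraph opens: "For adolescent participants over 12 years of age and less than 18 years of age". Protocol 4.2 defines adolescents as ≥12 to <18 years, and inclusion criterion 1 starts at 12.
- **Use of the grades.** SAP 4.6.3.1 counts participants whose maximum post-baseline grade exceeds their baseline grade, with separate counts for increases to Grades 3 and 4. A missing baseline grade is taken as 0. The normal-range shift summary covers only tests that DMID does not grade.

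**The concern.** A derivation rule should give every value one grade and the right direction, and a programmer who follows this table exactly gets neither in places. Severe leukopenia would appear in a line whose label says the count was high. A creatinine or urea ratio in a gap would be ungraded although a lower ratio is graded. Because these tests are DMID-gradable, the normal-range shift summary does not pick such a value up, so both categorical laboratory displays can miss it. Renal effects are a named potential risk in Protocol 2.3.1, so the creatinine grades should be clean. What is at stake is the accuracy of a few cells in safety tables.

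**Working it through.** The plan states no figure to reproduce here. The check codes the printed bands exactly (limits inclusive, > and < strict) and grades test values. It covers leukocytes, creatinine and urea, with AST/ALT as a control; other rows were not examined.

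**1. Leukocytes (/mm³)**

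| Count | Literal result |
|---|---|
| 500, 900, 999 | *Leukocytes (High)*, Grade 4 |
| 1000 to 3500 | no grade |
| 12,000 | *Leukocytes (High)*, Grade 1 |
| 31,000 | *Leukocytes (High)*, Grade 4 |

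Counts of 900 and 31,000 give identical output.

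**2. Ratios to ULN**

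| Test | Ungraded intervals | Examples |
|---|---|---|
| Adult creatinine | (1.5, 1.6), (3.0, 3.1) | 1.5 → Grade 1; 1.55 → none; 1.6 → Grade 2 |
| Urea | (2.5, 2.6), (5, 5.1) | 2.5 → Grade 1; 2.55 → none; 2.6 → Grade 2 |
| Adolescent creatinine | (1.7, 1.8), (2.4, 2.5) | from the printed limits |
| AST/ALT (control) | none | bands written with < limits |

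Share of the Grade 1–3 range left ungraded, as total gap width over range:
- adult creatinine: 0.2 / (6.0 − 1.1) = 4.1%
- urea: 0.2 / (10 − 1.25) = 2.3%
- adolescent creatinine: 0.2 / (3.5 − 1.0) = 8.0%

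These are shares of the scale, not of participants.

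**3. Can reported results fall in a gap?** The documents give no ULN, so a range is assumed.

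| Assumed ULN | First gap | Second gap |
|---|---|---|
| Creatinine 60 µmol/L | 91–95 | 181–185 |
| Creatinine 100 µmol/L | 151–159 | 301–309 |
| Creatinine 0.80 mg/dL | 1.21–1.27 | 2.41–2.47 |
| Urea 6.0 mmol/L | 15.1–15.5 | 30.1–30.5 |
| Urea 8.0 mmol/L | 20.1–20.7 | 40.1–40.7 |

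They can, at every ULN tried.

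**4. Effect on the grade-increase table (adult creatinine, × ULN)**
- Baseline normal, only abnormal post-baseline value 1.55: no grade, so the increase is not counted.
- Baseline 1.3 (Grade 1), later 1.55: no increase under the literal rule. It is still no increase if Grade 1 is extended to <1.6, but is an increase to Grade 2 if 1.55 is rounded half up to 1.6.
- Baseline 1.55, later 1.3: if the ungraded baseline is taken as grade 0, this is an increase from 0 to 1 although creatinine fell. That handling is an inference; the SAP rule speaks of a missing grade, not of a value outside all bands.

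**5. Age.** SAP 6.2.9 derives age as an integer, so a 12-year-old has age 12, which is not over 12. The choice of table can matter: 2.7 × ULN is adult Grade 2 (1.6–3.0) but paediatric Grade 3 (2.5–3.5).

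**The case against.** The strongest reply is that this is inherited and nearly harmless. The adult creatinine and urea bands are those of Protocol 10.12, and the SAP says its criteria are aligned with the global studies. A programmer may round to one decimal as a matter of course, and SAP 4.6.3.1 already orders a split by direction. Leukopenia is not hidden: a total count below 1000/mm³ implies neutrophils below 1000/mm³, which is at least Grade 2 under *Neutrophils (Low)* when the required differential is reported. The change-from-baseline summaries keep every value, and renal severity is also evaluated from creatinine clearance (SAP 6.2.2.2). The age wording sits under an adolescent heading and is plainly a slip.

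Most of this stands and limits the size of the point. It does not remove it, because the SAP states no rounding of the ratio and supplies no Low label for the split to use. The High label is the SAP's own addition to the protocol row.

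Three stronger inferences are not supported:
- **That the SAP closed such gaps elsewhere and overlooked these.** The enzyme < limits are already in the protocol table. The leukocyte limits of 13,001 and 15,001 removed overlapping endpoints, not gaps.
- **That a creatinine rising from Grade 1 into a gap is displayed as an improvement.** The table counts increases only and has no improvement category.
- **That every error is reassuring.** A baseline value in a gap can produce a false increase, and the leukocyte fault is one of direction, not of severity.

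**Conclusion.** The point holds as a minor specification fault. Followed literally, SAP 6.2.4.1 gives the wrong direction label to a leukocyte count below 1000/mm³, contrary to SAP 4.6.3.1, and no grade to creatinine and urea ratios inside two 0.1 × ULN intervals per scale. The age wording needs correcting. The conclusion rests on the absence of any rounding rule for the ratio and on the statement that only the numerical criteria are applied. How an ungraded baseline value is handled is not stated. The documents do not allow a count of affected participants, but it should be small: the gaps are narrow, and known renal impairment and clinically significant persistent granulocytopenia are exclusions. A reader should not infer that the renal safety assessment or the primary analysis is compromised.

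**What to change.** 1. **Leukocytes.** Move the <1000/mm³ criterion to its own *Leukocytes (Low)* line, with Grade 4 only, and leave >30,000/mm³ as Grade 4 in the High line.
2. **Ratios to ULN.** Keep the printed bands and state that, for creatinine and urea, the ratio is rounded to one decimal (half up) before it is graded. Apply the Grade 1 floor and the Grade 4 cut-off to the unrounded ratio. Otherwise rounding also moves those edges: an adolescent creatinine of 0.95 × ULN, within normal limits, would round to 1.0 and become Grade 1, and an adult 6.04 would round to 6.0 and drop from Grade 4 to Grade 3. Contiguous bands are an acceptable alternative. The two options can differ (1.55 is Grade 2 if rounded, Grade 1 if the band is extended to <1.6), so use whichever convention the global studies applied; the documents do not say which.
3. **Baseline.** With every value graded, the grade-0 rule applies only to a baseline that is truly missing; say so.
4. **Age.** Replace the adolescent wording with ≥12 to <18 years.

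The cost is a short SAP table edit and a few lines of derivation code. No new data are needed.

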#### Adults:

For adults, laboratory abnormalities will be graded according to the modified US National Institute of Allergy and Infectious Diseases Division of Microbiology and Infectious Diseases (DMID) criteria, which is aligned with the global studies (204989 and 212390). Laboratory results are converted to SI units.

HEMATOLOGY						
	Laboratory parameter	Display label	Grade 1	Grade 2	Grade 3	Grade 4
Hemoglobin	Hemoglobin	Hemoglobin (Low)	9.5 to 10.5 g/dL	8.0 to 9.4 g/dL	6.5 to 7.9 g/dL	<6.5 g/dL
Absolute Neutrophil Count	Neutrophils	Neutrophils (Low)	1000 to 1500 /mm 	750 to 999 /mm 	500 to 749 /mm 	<500 /mm 
Platelets	Platelets	Platelets (Low)	75,000 to 99,999 /mm 	50,000 to 74,999 /mm 	20,000 to 49,999 /mm 	<20,000 /mm 
White Blood Cells	Leukocytes	Leukocytes (High)	11,000 to 13,000 /mm 	13,001 to 15,000 /mm 	15,001 to 30,000 /mm 	>30,000 or <1000 /mm 
% Polymorphonuclear Leukocytes + Band Cells	NA	NA	>80%	90 to 95%	>95%	N/A
Abnormal Fibrinogen	NA	NA	Low: 100 to 200 mg/dL High: 400 to 600 mg/dL	Low: <100 mg/dL High: >600 mg/dL	Low: <50 mg/dL High: N/A	Fibrinogen associated with gross bleeding or with disseminated coagulation
Fibrin Split Product	NA	NA	20 to 40 mcg/mL	41 to 50 mcg/mL	51 to 60 mcg/dL	>60 mcg/dL
Prothrombin Time (PT)	NA	NA	1.01 to 1.25 × ULN	1.26 to 1.5 × ULN	1.51 to 3.0 × ULN	>3 × ULN
Activated Partial Thromboplastin (APTT)	NA	NA	1.01 to 1.66 × ULN	1.67 to 2.33 × ULN	2.34 to 3 × ULN	>3 × ULN
Methemoglobin	NA	NA	5.0 to 9.9%	10.0 to 14.9%	15.0 to 19.9%	>20%

N/A=not applicable; ULN=upper limit of normal.

CHEMISTRIES						
	Laboratory parameter	Display label	Grade 1	Grade 2	Grade 3	Grade 4
Hyponatremia	Sodium	Sodium (Low)	130 to 135 mEq/L	123 to 129 mEq/L	116 to 122 mEq/L	<116 mEq/L or abnormal sodium with mental status changes or seizures
Hypernatremia	Sodium	Sodium (High)	146 to 150 mEq/L	151 to 157 mEq/L	158 to 165 mEq/L	>165 mEq/L or abnormal sodium with mental status changes or seizures
Hypokalemia	Potassium	Potassium (Low)	3.0 to 3.4 mEq/L	2.5 to 2.9 mEq/L	2.0 to 2.4 mEq/L or intensive replacement therapy of hospitalization required	<2.0 mEq/L or abnormal potassium with paresis, ileus, or life-threatening arrhythmia
Hyperkalemia	Potassium	Potassium (High)	5.6 to 6.0 mEq/L	6.1 to 6.5 mEq/L	6.6 to 7.0 mEq/L	>7.0 mEq/L or abnormal potassium with life-threatening arrhythmia
Hypoglycemia	Glucose	Glucose (Low)	55 to 64 mg/dL	40 to 54 mg/dL	30 to 39 mg/dL	<30 mg/dL or abnormal glucose with mental status changes or coma
Hyperglycemia (nonfasting and no prior diabetes)	Glucose	Glucose (High)	116 to 160 mg/dL	161 to 250 mg/dL	251 to 500 mg/dL	>500 mg/dL or abnormal glucose with ketoacidosis or seizures
Hypocalcemia (corrected for albumin)	Calcium	Calcium (Low)	8.4 to 7.8 mg/dL	7.7 to 7.0 mg/dL	6.9 to 6.1 mg/dL	<6.1 mg/dL or abnormal calcium with life-threatening arrhythmia or tetany
Hypercalcemia (corrected for albumin)	Calcium	Calcium (High)	10.6 to 11.5 mg/dL	11.6 to 12.5 mg/dL	12.6 to 13.5 mg/dL	>13.5 mg/dL or abnormal calcium with life-threatening arrhythmia
Hypomagnesemia	Magnesium	Magnesium (Low)	1.4 to 1.2 mEq/L	1.1 to 0.9 mEq/L	0.8 to 0.6 mEq/L	<0.6 mEq/L or abnormal magnesium with life-threatening arrhythmia
Hypophosphatemia	Phosphate	Phosphate (Low)	2.0 to 2.4 mg/dL	1.5 to 1.9 mg/dL or replacement Rx required	1.0 to 1.4 mg/dL intensive therapy or hospitalization required	<1.0 mg/dL or abnormal phosphate with life-threatening arrhythmia

CHEMISTRIES						
	Laboratory parameter	Display label	Grade 1	Grade 2	Grade 3	Grade 4
Hyperbilirubinemia (when accompanied by any increase in other liver function test)	Bilirubin (when any of AST, ALT and ALP is greater than the upper limit of normal range at the same analysis visit)	Bilirubin (High)	1.1 to <1.25 × ULN	1.25 to <1.5 × ULN	1.5 to 1.75 × ULN	>1.75 × ULN
Hyperbilirubinemia (when other liver function tests are in the normal range)	Bilirubin (when all of AST, ALT and ALP are within the normal range at the same analysis visit)	Bilirubin (High)	1.1 to <1.5 × ULN	1.5 to <2.0 × ULN	2.0 to 3.0 × ULN	>3.0 × ULN
Blood urea nitrogen	Urea	Urea Nitrogen (High)	1.25 to 2.5 × ULN	2.6 to 5 × ULN	5.1 to 10 × ULN	>10 × ULN
Hyperuricemia (uric acid)	NA	NA	7.5 to 10.0 mg/dL	10.1 to 12.0 mg/dL	12.1 to 15.0 mg/dL	>15.0 mg/dL
Creatinine	Creatinine	Creatinine (High)	1.1 to 1.5 × ULN	1.6 to 3.0 × ULN	3.1 to 6.0 × ULN	>6 × ULN or dialysis required

Rx=therapy; ULN=upper limit of normal

